10.6 Analyses

A Statistical Analysis Plan (SAP) will be developed that describes, in detail, the analyses to address the study's primary and secondary objectives in both phase II and phase III. The following provides an outline of the methods for the main comparisons between randomized groups, particularly for the primary outcome measures in each of phase II and phase III.

All analyses involving randomized comparisons will include all randomized participants who started an investigational agent or the concurrent placebo, according to a modified intention-to-treat approach. This should not introduce bias into the randomized comparison because of the use of a placebo. However, if evaluation of an investigational agent involves combining different placebos (i.e., because the study is partially blinded, with different placebos for different investigational agents), then consideration of the sensitivity of results to the possibility of different outcomes according to type of placebo taken will be considered; details will be provided in the SAP.

A general principle in all analyses is that outcomes among participants randomized to receive a specific investigational agent will be compared to outcomes among participants who were eligible to have been randomized (in the two-step randomization process) to the investigational agent but who were randomized instead to receive any of the placebos available at the time. This ensures that the comparison is restricted to concurrently randomized participants eligible to have taken the investigational agent of interest. **In particular, the analysis of phase II will include any higher risk participants enrolled under earlier versions of the protocol.**

10.6.1 Primary Outcome Measures for Phase II

Virologic Outcome: Unquantifiable SARS-CoV-2 RNA in NP Swabs

Descriptive statistics will be used to describe the proportion of participants with RNA <LLoQ at each scheduled measurement time. Because of uncertainty about whether hospitalization might be driven by immunologic factors rather than virologic factors, the main analysis will not impute virologic outcome if results are not available because of hospitalization (though the sensitivity of this issue will be explored by considering an imputation of having quantifiable virus during hospitalization). For (frequentist) inference in presenting results, a repeated measures analysis will be undertaken across the scheduled

measurement times using a binary regression model fitted using the generalized estimating equation approach with an independence working correlation structure, and two-sided 5% Type I error rate applied to a Wald-type test of the treatment by time interaction term (time included with indicator variables for each evaluation time).

Clinical Outcome: Symptom Duration

Symptom durations will be compared between study groups using a two-sided Wilcoxon test with a 5% Type I error rate taking account of censoring, with descriptive summaries of the distribution of symptoms durations among participants.

Safety and Tolerability: Grade 3 or Higher AE

Safety and tolerability will be evaluated by estimating the proportion of participants with new Grade 3 or higher AE(s) by study day 28, and will be compared between groups using binary regression.

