1.0 STUDY OBJECTIVES

1.1 Co-Primary Objectives

- 1.1.1 Phases II and III: To evaluate safety of the investigational agent.
- 1.1.2 Phase II: To determine efficacy of the investigational agent to reduce the duration of COVID-19 symptoms through study day 28.
- 1.1.3 Phase II: To determine the efficacy of the investigational agent to increase the proportion of participants with nasopharyngeal (NP) SARS-CoV-2 RNA below the lower limit of quantification (LLoQ) at study days 3, 7, 14, and 28.
- 1.1.4 Phase III: To determine if the investigational agent will prevent the composite endpoint of either hospitalization or death through study day 28. Hospitalization is defined as ≥ 24 hours of acute care, in a hospital or similar acute care facility, including Emergency Rooms or temporary facilities instituted to address medical needs of those with severe COVID-19 during the COVID-19 pandemic.

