10.2.1 Phase II: Primary Outcome Measures

10.2.1.1 Clinical (Symptom Duration): Duration of targeted COVID-19 associated symptoms from start of investigational agent (day 0) based on self-assessment. Duration defined as the first of two consecutive days when any symptoms scored as moderate or severe at study entry (pre-treatment) are scored as mild or absent, AND any symptoms scored as mild or absent at study entry (pre-treatment) are scored as absent. The targeted symptoms are feeling feverish, cough, shortness of breath or difficulty breathing, sore throat, body pain or muscle pain or aches, fatigue (low energy), headache, chills, nasal obstruction or congestion (stuffy nose), nasal discharge (runny nose), nausea, vomiting, and diarrhea. Each symptom is scored daily by the participant as absent (score 0), mild (1), moderate (2) and severe (3).

10.2.1.2 Virologic: At each of days 3, 7, 14, and 28, quantification (<LLoQ versus \geq LLoQ) of SARS-CoV-2 RNA from site-collected NP swabs.

10.2.1.3 Safety: New Grade 3 or higher AE through 28 days.

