10.4 Sample Size

10.4.1 Phase II

The phase II evaluation of an investigational agent involves the comparison of two primary outcomes (quantifiable SARS-CoV-2 RNA at days 3, 7, 14, and 28; and symptom duration) among participants randomized to that agent versus participants concurrently randomized to the placebo. This evaluation will involve approximately 110 participants randomized to the investigational agent and approximately 110 participants concurrently randomized to the control group for that agent (combined across one or more concurrently randomized placebo arms). The choice of sample size has been chosen to give high power to identify an active agent based on the primary virologic outcome so we describe that first. The phase II study is not specifically designed to have a high level of power for the symptom duration outcome, but we illustrate the anticipated power to detect a range of reductions in median symptom duration. As this is the phase II component of the study and hence there will be further evaluation of an agent that graduates to phase III, no adjustment is made for the multiplicity of outcomes being assessed for a given investigational agent (or across investigational agents).

Virologic Outcome

The percentage of participants with quantifiable SARS-CoV-2 RNA in NP swabs will be compared between an investigational agent and placebo control at each of days 3, 7, 14, and 28. It is uncertain what might be the percentage <LLoQ at each of these times in the population being studied, and this percentage is likely to depend on the time since onset of symptoms at which participants are enrolled. However, a 20% absolute increase in percentage of participants with SARS-CoV-2 RNA <LLoQ is thought to be relevant. For example, in a clinical trial comparing the combination of interferon beta-1b, ribavirin, lopinavir/ritonavir (n=86) to lopinavir/ritonavir alone (n=41) in hospitalized COVID-19 patients in China, there was both a difference in clinical outcomes and more than a 20% reduction in undetectable virus at about 7 days (with the caveat that this does not establish that a difference in virologic outcome is a surrogate for a difference in clinical outcome) [8]. The median time to undetectable virus was 7 versus 14 days in this trial (based on daily NP swabs obtainable in the hospitalized setting), indicating that 50% of participants were undetectable at 7 and 14 days in the two groups.

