With a phase II sample size of 110 participants assigned to an investigational agent and a similar number concurrently assigned to placebo, we assume that about 100 participants in each group will have NP swabs available at a scheduled measurement time. Table 10.4.1-1 shows the power to detect a 20% absolute increase in percentage of participants with unquantifiable virus for a range of percentages with unquantifiable virus in the placebo arm. The power was calculated for the comparison of two proportions using a normal

approximation to the binomial distribution and unpooled variance, with two-sided Type I error rate of 5%. A power of over 82% is achieved regardless of the percentage of participants with unquantifiable virus in the control group. A sample size of 100 per group with NP swabs would also provide reasonable precision in estimating the absolute difference between groups in percentage with unquantifiable virus: for example, the width of a two-sided 95% confidence interval would be no more than $\pm 13.6\%$ around the observed difference, and the width of a two-sided 90% confidence interval would be no more than $\pm 11.4\%$.

Table 10.4.1-1: Power to Detect a 20% Absolute Increase in % with SARS-CoV-2 RNA <LLoQ for Various Percentages Unquantifiable in Control Group (calculated in PASS15 software)

Control Group: Number with NP Swabs	Investigational Group: Number with NP Swabs	Percentage Unquantifiable in Investigational Arm	Percentage Unquantifiable in Placebo Arm	Power (%)
100	100	30	10	95.5
100	100	40	20	88.5
100	100	50	30	83.9
100	100	60	40	82.3
100	100	70	50	83.9
100	100	80	60	88.5
100	100	90	70	95.5

The duration of symptoms from the start of investigational agent through 28 days of follow-up will be compared between an investigational agent and placebo control.

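### The phase II primary virologic test asks whether the treatment effect differs between visits, not whether the agent has an effect, and the stated power is not the power of that test

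*Protocol*

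**What the plan says.** Objective 1.1.3 of the protocol is "to increase the proportion of participants with nasopharyngeal (NP) SARS-CoV-2 RNA below the lower limit of quantification (LLoQ) at study days 3, 7, 14, and", the last day listed being 28. The outcome in section 10.2.1 is defined by visit ("At each of days 3, 7, 14, and 28, quantification"), and day 0 is not among the visits listed.

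Section 10.4.1 says that the percentage with quantifiable RNA "will be compared between an investigational agent and placebo control at each of days 3, 7, 14, and 28" and that "a 20% absolute increase in percentage of participants with SARS-CoV-2 RNA <LLoQ is thought to be relevant". It sizes phase II mainly on this outcome. It computes power for two proportions with 100 swabs per group at a scheduled visit, unpooled variance and two-sided 5% error, and concludes: "A power of over 82% is achieved regardless of the percentage of participants with unquantifiable virus in the control group".

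Section 10.6.1 describes the proportions at each visit, then gives one inferential procedure: a "binary regression model fitted using the generalized estimating equation approach with an independence working correlation structure", with a "two-sided 5% Type I error rate applied to a Wald-type test of the treatment by time interaction term". The visits enter the model as a factor ("time included with indicator variables for each evaluation time"). It states no main-effect test, joint test or per-visit test of this outcome. Section 10.6.3 adds per-visit Wilcoxon tests, but these are for quantitative RNA level, a secondary outcome.

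**The concern.** When a model has a treatment term, visit indicators and their product, the product terms measure how the effect at three visits departs from the effect at the fourth. Testing that they are zero tests equality of the four effects. Four equal effects satisfy that null hypothesis whether they are all zero or all large.

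The stated primary test therefore does not address the stated primary objective. An agent that meets the 20-point target at every visit could be reported as non-significant on the outcome that determined the sample size. Conversely, a significant interaction does not by itself show benefit, since an early gain with a late loss produces one too. A reader of 10.4.1 would also take the power of over 82% to apply to the analysis in 10.6.1.

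**Working it through.** **Inputs from the protocol.** 100 evaluable per group per visit; visits at days 3, 7, 14 and 28; 20-point target; two-sided 5%; visit indicators; GEE with independence working correlation. **Assumed, because not given:** placebo percentage below LLoQ at each visit, correlation between visits, and the link.

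**1. The plan's own figure.** Power = Φ(0.20/SE − 1.96), with SE = √[p1(1−p1)/100 + p0(1−p0)/100].
- 60% v 40%: SE = √(0.0024 + 0.0024) = 0.0693; 0.20/0.0693 − 1.96 = 0.93; power 82.3%.
- 30% v 10%: SE = √(0.0021 + 0.0009) = 0.0548; 0.20/0.0548 − 1.96 = 1.69; power 95.5%.

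All seven rows of Table 10.4.1-1 reproduce (82.3% to 95.5%).

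**2. The test in 10.6.1.** Let d₁ to d₄ be the treatment differences at the four visits on the model's scale, with variances v₁ to v₄ and weights w = 1/v. For independent visits the noncentralities are:
- joint test of all four differences (4 df): λ₄ = Σw·d²
- interaction (3 df): λ₃ = Σw·d² − (Σw·d)²/Σw

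If every d is the same, λ₃ = 0 whatever its size, and the test rejects at its 5% level.

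*Flat example, 40% v 60% at every visit, identity link.* v = 0.0048, so λ₄ = 4 × 0.04/0.0048 = 33.3 and λ₃ = 0. Power: joint 99.9%, interaction 5.0%.

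*Fading example, placebo 10/30/60/90%, gains +20/+20/+10/0, identity link.* v = 0.0030, 0.0046, 0.0045, 0.0018, so w = 333.3, 217.4, 222.2, 555.6.
- Σw·d² = 13.33 + 8.70 + 2.22 + 0 = 24.25
- Σw·d = 132.4 and Σw = 1328.5, so λ₃ = 24.25 − 132.4²/1328.5 = 11.06

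Power: interaction 81%, joint 99%.

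**3. Range over assumed scenarios.** The first, second, fourth and fifth rows are simulations of 5,000 trials each at latent between-visit correlation 0, 0.5 and 0.7. The third row is 2,500 trials per scenario at 0.3 to 0.6. The last four rows are analytic, with independent visits.

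| Scenario (placebo % at the four visits) | Interaction, 3 df | Joint, 4 df |
|---|---|---|
| +20 points throughout, 10/30/50/70 | identity 6%; log 56–62%; logit 17–27% | 98.5–100% |
| +20 points throughout, 20/35/50/60 | identity 5–6%; log 23–25%; logit 6–7% | 94–100% |
| +20 points throughout, 30/40/50/60 | identity 6%; log 13%; logit 6–7% | 95–99% |
| Constant risk ratio 1.5, 20/30/40/60, log link | 5% | 99–100% |
| Constant odds ratio 2.25, 10/30/50/70, logit link | 5% | 83–99% |
| +20 points throughout, flat 40 | 5% on any link | over 99% |
| +20/+20/+10/0, 10/30/60/90 | identity 81%; log 96%; logit 51% | 99%; 97%; 98% |
| +10/+20/+20/0, 10/30/60/90 | identity 77%; log 93%; logit 29% | 98%; 97%; 97% |
| 0/+20/+10/0, 10/30/60/90 | identity 66%; log 68%; logit 33% | 76%; 72%; 73% |

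The 1-df average test has 98% to 100% power for +20 points throughout and 94% to 100% for the constant odds ratio.

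**The case against.** **The constant-benefit case is not what the protocol assumes.** This stands in part. Section 10.4.1 calls the visit percentages uncertain. Section 2.1 reports about a quarter of persons still shedding at 3 weeks, so a 20-point gain at day 28 may meet a ceiling (indicative only, since shedding is not the same as being above the LLoQ). A narrowing benefit gives the interaction test real power, as the fading scenario shows. A reader might infer that an agent with the same absolute benefit at every visit has almost no chance of a positive result. That is exact only if the benefit is constant on the model's own scale: a constant 20 points reaches about 60% power under a log link with placebo 10/30/50/70. Even so, an illustration with exponential clearance at the medians cited in 10.4.1 (7 v 14 days) gives the interaction test 18% to 41% and the joint test 99% to 100%.

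**The wording may be loose.** Section 10.6 calls itself an outline. If the model had visit-specific treatment terms and no treatment main effect, the product terms would form the 4-df joint test. The text does not say so, and 82% would not be the power of that test either.

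**The power table is not wrong.** This stands. A reader might infer an arithmetic error, but 10.4.1 describes a comparison at one scheduled visit and the figures are right for it. Nor is the unnamed link a defect, since a protocol may leave that to the SAP.

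**Consequences are bounded.** A reader might infer that a non-significant interaction would end an agent's development. The protocol does not support that. Per-visit proportions are described, RNA levels and AUC are tested as secondary outcomes, section 2.2 makes graduation a committee judgement on several kinds of evidence, and section 3.2 defers future criteria. None of this repairs the primary test.

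**Conclusion.** The point holds as a conflict within the protocol. Section 10.6.1 fixes the tested term and its error rate, and that term does not answer objective 1.1.3 or match the comparison powered in 10.4.1. It is not merely detail awaiting the SAP.

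That a benefit constant on the model's scale is detected only at about 5% follows from the algebra and needs no assumed profile. It rests on the plain reading: main effects in the model and only the four post-entry visits analysed. The other figures do depend on assumed profiles, correlations and link. A constant 20-point gain gives about 5% to 60%, below 82% in every profile tried. A fading gain gives 51% to 96%, so in some cases the interaction test exceeds 82%. The joint test was at least as powerful in every scenario shown. The correction should be made before the phase II virologic analysis is finalised.

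**What to change.** In 10.6.1, replace the interaction test with one of these at two-sided 5%:
- a Wald test that the treatment differences at days 3, 7, 14 and 28 are all zero (treatment main effect plus interactions, 4 df), or
- a 1-df test of the treatment effect averaged over the four visits.

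The choice should follow the pattern expected. The 4-df test keeps power when effects vary, but it has no direction, so it must be read with the visit-specific estimates and their intervals. It also pays for its extra degrees of freedom: for a 20-point effect on day 7 only (placebo 30/40/50/60, latent correlation 0.3 to 0.6), its simulated power is 61% to 75%. The 1-df test has a direction but is diluted by a short-lived effect. Keep the interaction only to describe change over time.

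In 10.4.1, say that 82% to 95% is power at a single visit, and add the power of the chosen overall test under stated placebo profiles and correlations.

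Cost: a few sentences in the protocol, matching text in the SAP and one power calculation. Sample size, visits and data collection need not change.

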10.6.2 Primary Outcome Measures for Phase III

Hospitalization/Death

The cumulative proportion of participants hospitalized or dying during the first 28 days of follow-up will be estimated for each randomized group using Kaplan-Meier methods to take account of losses to follow-up. The difference between randomized groups in the estimated log cumulative proportion will be calculated and the variance for this difference will be obtained using Greenwood's formula. Two-sided 95% confidence intervals (adjusted for multiple interim analyses) and associated p-value for the test of no difference between groups will then be obtained.

Participants who prematurely discontinue the study, who are not able to be contacted by the site to ascertain outcomes after discontinuation, will have follow up censored at the date of last known status.

The above analysis assumes that losses to follow-up are non-informative. As a sensitivity analysis of this assumption, causal inference methods, specifically inverse probability of censoring, may be used.

Safety and Tolerability: Grade 3 or Higher AE

Safety and tolerability will be evaluated by estimating the proportion of participants with new Grade 3 or higher AE(s) by study day 28, and will be compared between groups using binary regression.

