10.4.2 Phase III

For **the investigational agent currently in phase III evaluation**, the phase III aspect of the study is designed to evaluate the efficacy of **the agent** to reduce the proportion of participants hospitalized or dying by 28 days after starting investigational agent in outpatient adults diagnosed with COVID-19 compared to those receiving placebo. The primary analysis will focus on comparing the ratio of proportions because of the uncertainty in knowing what the hospitalization/death proportion will be.

A total of approximately 421 participants will be randomized to receive the agent and approximately 421 participants will be concurrently randomized as the placebo control. This sample size includes the enrollment that occurred during the phase II evaluation **of this agent**. With 842 participants, the study has 90% power to detect a relative reduction of 50% in the proportion of participants hospitalized/dying between the study groups (investigational agent versus placebo), using a two-sided Type I error rate of 5%, using the following assumptions:

- Proportion hospitalized/dying in the placebo arm is 15%. This proportion is based on that observed in preliminary data in a similar higher risk outpatient population in the BLAZE-1 trial [15].
- Targeted 50% reduction is plausible based on the observed effect seen in the BLAZE-1 trial for both a single mAb and for a dual combination mAb [15]. Three interim analyses and one final analysis, equally spaced, with stopping guideline for efficacy of an agent versus placebo determined using the Lan-DeMets spending function approach with an O'Brien and Fleming boundary.

- Non-binding stopping guideline for futility using a moderately aggressive Type II error spending function, specifically a Gamma (-2) spending function [15], implemented using the Lan-DeMets spending function approach. Further details about these stopping guidelines are in section 10.5.
- Allowance for 5% of participants to be lost-to-follow-up prior to being hospitalized or dying.

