10.5.2 Phase III **Evaluation**

A NIAID-appointed DSMB will undertake reviews of interim data from the study to help ensure the safety of participants in the study, and to recommend changes to the study including termination or modification for safety reasons or if there is persuasive evidence of efficacy or lack of efficacy of an investigational agent versus placebo in preventing hospitalizations and deaths. It is not intended, however, to terminate evaluation of an agent early for efficacy based on symptom outcome measures. The DSMB may also recommend termination or modification of the study if it appears futile on statistical or operational grounds to continue the study as designed. The operation of the DSMB is governed by the NIAID DSMB Charter.

At each interim review of an investigational agent, the DSMB will review summaries of data by randomized treatment arm for the primary outcome of hospitalization/death, the secondary outcome of death, losses to follow-up, and adverse events (including early discontinuation of investigational agent).

Stopping Guideline for Efficacy and Timing of Interim Efficacy Analyses

Unless otherwise recommended by the DSMB, it is intended that the DSMB review three interim analyses of safety and efficacy data for an investigational agent versus placebo at **the following times (corresponding to approximately 25%, 50% and 75% of the expected maximal information):**

1. The first interim analysis for Phase III will be when 220 participants from the two groups combined have been followed for the primary outcome assessed at day 28 (this will likely then be the same hospitalization/death information as used in the phase II graduation analysis), or when

- approximately 24 participants in the two groups combined have been hospitalized or have died;
2. The earlier of when approximately 421 participants from the two groups combined have been followed for the primary outcome assessed at day 28, or when approximately 48 participants in the two groups combined have been hospitalized or have died; and
 3. The earlier of when approximately 632 participants from the two groups combined have been followed for the primary outcome assessed at day 28, or when approximately 72 participants in the two groups combined have been hospitalized or have died.

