- an agent may be discontinued for statistical futility based on evidence of lack of effect or very limited effect compared with placebo. For the purposes of evaluating this, a moderately aggressive Type II error spending function will be used, specifically the Gamma (-2) spending function implemented using the Lan-DeMets spending function approach [16].

[Figure 10.5.2-1](#) illustrates the stopping guidelines for both efficacy and futility assuming four equally spaced analyses (noting that the first interim analysis is at **approximately** 26% of maximal information). The left panel shows the stopping guidelines in terms of critical values for a z-test statistic comparing an agent to placebo for the four analyses. The right panel shows the stopping guidelines in terms of observed differences in proportions for the scenario when the observed proportion in the placebo control arm is 0.15 (i.e., 15%). In both panels, greater negative values favor greater effects of an investigational agent versus placebo, and values in the blue area suggest stopping for efficacy whereas values in the pink area suggest stopping for futility. As an example, focusing on the right-hand panel, if the observed proportion for placebo was 0.15 (i.e., 15%) at the first interim analysis, an absolute difference in proportions of 0.025 or larger (i.e. favoring placebo by 2.5%) at the first interim analysis would suggest stopping for futility. At the second interim analysis, an absolute difference of -0.011 (i.e., -1.1%) or smaller (i.e. negative but closer to zero than -1.1%, or positive hence favoring placebo) would suggest stopping for futility.

[figure not shown]

Figure 10.5.2-1: Stopping Boundaries for Efficacy and Futility

Modifying or Stopping the Study for Operational Futility

The DSMB will also monitor operational futility. With respect to operational futility, the DSMB may recommend modification or termination of the study if the proportion hospitalized/dying in the control group is much lower than expected in designing the trial. In addition, the DSMB will monitor the loss to follow-up (LTFU) rate. As a benchmark, an overall LTFU rate of more than 10% would be cause for concern.

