10.6.3 Secondary Outcomes

The cumulative proportion of participants dying during the first 28 days of follow-up, and through to 24 weeks, and the cumulative proportion hospitalized/dying through

to 24 weeks will be analyzed in a similar manner to the phase III primary outcome. Analysis of the proportion of participants with new Grade 2 or higher AE(s) by day 28 in phase II, and new Grade 3 or higher AE(s) by week 24 in phase III, and the proportion with progression of symptoms, will be undertaken using the same approach as for the primary safety analysis.

The duration of time to self-reported return to usual health will be analyzed using similar methods as for the analysis of symptom durations.

The AUC virologic outcome, COVID-19 severity ranking, will be compared between arms using a Wilcoxon test, with descriptive summaries of the distribution of these outcome measures among participants.

Levels of SARS-CoV-2 RNA on days 3, 7, 14, and 28 will be compared between arms using non-parametric Wilcoxon rank-sum tests and descriptive statistics, separately at each scheduled measurement time (considering RNA results below assay limit as the lowest rank).

Descriptive summaries of clinical outcomes among those hospitalized will be provided by arm, recognizing that this would not be a randomized comparison, if restricted to participants who were hospitalized.

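### The phase III log-ratio test cannot cross the efficacy boundary at a 24-event first look and has no value when an arm has no events, although the sample size and worked stopping limits come from the difference in proportions

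*Protocol*

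**What the plan says.** **Effect measure and test.** Protocol 10.4.2 states: "The primary analysis will focus on comparing the ratio of proportions because of the uncertainty in knowing what the hospitalization/death proportion will be". Section 10.6.2 then fixes the statistic: "The difference between randomized groups in the estimated log cumulative proportion will be calculated". The same section settles its standard error: "the variance for this difference will be obtained using Greenwood's formula". The proportions are Kaplan-Meier estimates at day 28.

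**Sizing.** Section 10.4.2: "With 842 participants, the study has 90% power to detect a relative reduction of 50" percent, "using a two-sided Type I error rate of 5%, using the following assumptions". The assumptions are 15% on placebo, four equally spaced analyses, a Lan-DeMets O'Brien-Fleming efficacy boundary, a non-binding Gamma(-2) futility boundary and 5% loss to follow-up.

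**Monitoring.** Section 10.5.2 places the first look at 220 participants followed to day 28, or when "approximately 24 participants in the two groups combined have been hospitalized or have died". The left panel of Figure 10.5.2-1 gives the guideline as critical values of a z-statistic that is not named. For the other panel, "The right panel shows the stopping guidelines in terms of observed differences in proportions", at an observed placebo proportion of 0.15. The worked futility limits are +0.025 at the first look and -0.011 at the second.

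**Death.** Section 10.6.3 has "The cumulative proportion of participants dying during the first 28 days of follow-up" analysed like the phase III primary outcome. Section 10.5.2 also allows the DSMB to apply the O'Brien-Fleming guideline to death.

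**The concern.** A z-boundary can be applied to any statistic that is close to normal. The log ratio with a Greenwood variance is not close to normal when one arm has very few events. Its standard error grows as that arm empties, so stronger evidence can give a smaller z, and at zero events neither the estimate nor its variance exists. The O'Brien-Fleming value is highest at the first look, where events are fewest.

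If the agent were far better than designed for, a DSMB applying the stated statistic at about 24 events would find the boundary uncrossed, or would have no statistic at all, while a comparison of proportions could say stop. For death, the prescribed estimate might not exist even at the final analysis. The DSMB is also given two futility differences that do not match the z-boundary at the placebo rate they are stated for.

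**Working it through.** **Inputs.** From Protocol 10.4.2 and 10.5.2: 15% v 7.5%, 421 per arm, 5% loss, 220 participants (110 per arm) or about 24 events at look 1. Boundaries were recomputed at 0.025 per side, with z positive when the agent is better:
- Efficacy: 4.24 (26% information) or 4.33 (25%) at look 1, then 2.963, 2.359 and 2.014.
- Futility: -0.579 (26% information), 0.350 and 1.199.
- Drift for 90% power: 3.378.

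**1. Reproduce 421.**
- Unpooled variance of the difference: 0.15 × 0.85 + 0.075 × 0.925 = 0.196875.
- n = 3.378² × 0.196875 / 0.075² = 399.4 evaluable per arm.
- 399.4 / 0.95 = 420.4, so 421. This is the protocol's figure.
- On the log-ratio scale the variance is 0.85/0.15 + 0.925/0.075 = 18.0, so n = 3.378² × 18.0 / (ln 2)² = 427.5 evaluable, or 451 per arm after loss. The sizing therefore used the difference.

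**2. Does this cost power?** Simulating the four-look design at about 400 evaluable per arm with futility followed gives about 90.2% on the log ratio and 90.5% on the difference. The cost is negligible.

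**3. First look with 24 events, 110 per arm, no censoring.**
- Log-ratio z = ln(x/y) / √(1/x + 1/y − 2/110).
- Difference z = (x − y)/110 divided by its unpooled or pooled standard error.

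| Placebo v agent | Log-ratio z | Difference z, unpooled | Difference z, pooled |
|---|---|---|---|
| 24 v 0 | undefined | 5.54 | 5.19 |
| 23 v 1 | 3.10 | 5.02 | 4.76 |
| 22 v 2 | 3.30 | 4.52 | 4.33 |
| 21 v 3 | 3.23 | 4.03 | 3.89 |

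No split reaches 4.24 on the log ratio. With 60 to 421 per arm the maximum stays between 3.26 and 3.35. Note that 23 v 1 scores lower than 22 v 2.

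**4. When can it cross?** With 110 per arm, crossing needs about 39 events (for example 36 v 3) at 26% information, or 41 (38 v 3, z = 4.34) at 25%. About 25 events are expected at the design rates: 110 × (0.15 + 0.075) = 24.75.

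**5. Probability of crossing 4.24 at look 1.** Exact binomial, 15% on placebo, 110 per arm:

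| True reduction | Difference (pooled to unpooled) | Log ratio |
|---|---|---|
| 50% (design) | 0.3% to 0.5% | about 1 in a million |
| 80% | 7% to 11% | about 2 in a million |
| 90% | 19% to 28% | about 1 in a million |

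The chance that the agent arm is empty at this look is 0.97^110 = 3.5% at an 80% reduction and 0.985^110 = 19% at 90%.

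**6. Later looks.** With 48 events the boundary is crossed at 35 v 13 (log ratio) or 34 v 14 (difference); with 72 events, at 46 v 26 on both. The problem is confined to few events.

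**7. Death.** The protocol gives no death rate. Assuming 0.25% to 0.5% on the agent with 421 participants, the chance of no deaths in that arm is 0.9975^421 = 35% to 0.995^421 = 12%.

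**8. Futility differences.**
- Design variance: 0.579 × √(0.196875/104) = 0.025 and 0.350 × √(0.196875/200) = 0.011. These are the stated magnitudes (104 and 200 are 26% and 50% of 400 evaluable).
- With 15% observed on placebo and the agent at 15% + d, solve |d| / √{[0.15 × 0.85 + (0.15 + d)(0.85 − d)]/n} = |z|. For n = 110 and z = -0.579, d is about +0.029: 0.029/√(0.2745/110) = 0.58. For n = 210.5 and z = 0.350, d is about -0.012: 0.012/√(0.2465/210.5) = 0.35. The log-ratio scale gives the same two values.

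**The case against.** **The guideline is formally a z-boundary.** The difference scale appears only as an illustration, and information time is left to the SAP. This stands: the protocol does not instruct the DSMB to monitor on the difference scale. It does name the log-ratio statistic as the test, and that is the one that fails with few events.

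**A reader might infer that early stopping is impossible whatever the data.** The documents do not support that. The first look is at 220 participants or about 24 events, without the earlier-of wording used for the next two looks, so 39 to 41 or more events could be present and could cross. The impossibility belongs to the 24-event look. The guideline is also not binding on the DSMB.

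**A reader might infer that the trial is undersized,** because the large-sample formula gives 451 per arm on the log ratio, or about 88% power at 421. Simulation does not bear this out.

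**A reader might extend the point to the phase II hospitalization/death outcome.** Section 10.6.3 assigns this method to death and to the 24-week composite; no section assigns it to the phase II 28-day composite.

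**At the design effect almost nothing is lost.** Correct: look 1 is nearly uncrossable on any scale at a 50% reduction. The look may also be past, since 10.5.2 expects it to coincide with the phase II graduation data and the agent has already graduated; that is an inference.

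**The ratio has a stated rationale, and a zero-event rule may sit in the SAP.** Both are fair. The ratio can remain the reported effect, and a SAP rule would still have to depart from the statistic fixed here.

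**An unpooled Kaplan-Meier difference is no cure.** Also right: Greenwood gives an empty arm zero variance, which inflates z (5.54 against 5.19 pooled for 24 v 0).

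**Conclusion.** The point holds in limited form. The stated test differs from the statistic behind the sample size and worked limits, and it fails or is undefined where the effect is strongest or an arm is empty. At a 24-event first look its maximum is 3.30 against 4.24 to 4.33. The practical loss is a 7-11% or 19-28% chance of an early efficacy signal if the true reduction is 80% or 90%, and next to nothing at the 50% design effect. Power, later looks and the choice between scales for futility are essentially unaffected. For death, an empty agent arm arises in 12% to 35% of trials under the assumed rates. The two stated futility differences are slightly off, by 0.4 and 0.1 percentage points on a non-binding rule, because they use the design variance rather than the observed 15% scenario they are stated for.

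This rests on equal arms, no censoring in the first-look enumeration, 0.025 per side, and assumed death rates. At 4.33 instead of 4.24 the difference-scale chances fall somewhat (for a 50% reduction, 0.2% to 0.5%); the log-ratio result does not change.

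**What to change.** In Protocol 10.5.2 and 10.6.2, name one statistic for monitoring and testing: a score-type statistic using the null variance, defined when an arm has no events. Do not substitute an unpooled Greenwood difference.

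Keep the ratio with its confidence interval as the reported effect. State that a score or exact interval is used when an arm has few or no events, and apply the same rule to death in 10.6.3.

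Restate the two futility differences for the chosen statistic, or label +0.025 and -0.011 as based on the design variance.

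The cost is wording in three sections and a change to the DSMB report programs; the sample size need not change. The downside is that the test and the headline ratio would be on different scales, which one sentence can explain.
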